This pilot trial will treat up to 10 liver transplant recipients who are ≤65 years of age, a minimum of 2 years but no more than 4 years post primary liver transplantation for non-autoimmune conditions, have had no evidence of transplant rejection, and have no current evidence of liver allograft dysfunction or viral hepatitis.

Study objectives include (1) determine the efficacy of the administration of low dose IL-2 to promote Treg cell expansion; (2) assess the safety and efficacy of low dose IL-2 in a liver transplant recipient cohort; (3) investigate the percent change of peripheral blood Treg cells and change in phenotype and function of Treg cells in response to low dose IL-2 in a liver transplant recipient cohort.

Study Scheme:

Study Procedure:

Screening (S0):

After obtaining informed consent the following screening procedures will be completed:

- Full history and medical record review
- Physical examination including height and weight
- Vital signs (blood pressure, heart rate and temperature)
- Blood (approximately 20 milliliters) will be drawn for
 - ✓ liver function panels (AST, ALT, ALP, Bilirubin, Albumin) and kidney function panels (Na, K, Cl, CO₂, Creatinine, Glucose, Ca) if not previously obtained within 1 month of screening
 - ✓ viral hepatitis and autoimmune panels (HBV sAg, HCV Ab, ANA, ASMA IgG) if not previously obtained within 6 months of screening
 - ✓ serum pregnancy test for women of child bearing potential (WOCBP)
- Fibroscan if liver biopsy/fibroscan results not obtained within 1 year of screening
- ECG if not obtained within 3 months of screening

Subjects with liver panel results <2xULN, serum creatinine <1.5 ULN; no evidence of viral hepatitis or

autoimmunity, no evidence of pregnancy, absence of advanced liver fibrosis, no history of seizure disorder and no evidence of cardiac disease will proceed with the study (see Inclusion/Exclusion criteria in section below).

Baseline/Treatment Visit Day 1 (W0):

Subjects will return to clinic to complete baseline measures and begin study treatment:

- Review of any new health problems, current medication and vital sign measures;
- Blood draw (approximately 35 milliliters) for
 - ✓ CBC with differential,
 - ✓ liver and kidney function panels,
 - ✓ immune cell counts ,
 - ✓ T cell exhaustion phenotyping,
 - ✓ serum IL-2 levels,
 - ✓ CNI trough levels,
 - ✓ presence of donor specific antibodies (DSAs)
 - ✓ presence of anti-IL-2 antibodies

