Treatment: Subjects will start very low dose **IL-2 subcutaneous injections at a once per day dose of 0.3 million IU/mL per square meter body surface area (BSA) for 4 weeks.** Study staff will instruct subjects and/or identified care providers (e.g. friend or spouse) on subcutaneous injection technique.

The first study dose will be administered in the BIDMC Harvard-Thorndike Clinical Research Center. Subjects will remain in house for 2 hours of observation to monitor drug tolerability and adverse events.

Subjects will be given a paper calendar to record their self-administration of the study drug. Subjects will record the time of injections each day and bring the study calendar and all unused drug to all study visits. (see Calendar attached)

Treatment (D3):

Subjects will return to clinic on Day 3 for evaluation of adherence to treatment and staff observation of proper injection technique (for Dose 3) and the following measures will be obtained:

- Review of any new health problems, current medications
- Vital signs
- Blood draw (approximately 10 milliliters) for liver and kidney function panels

Treatment (W1, W2, W3, W4)

Subjects will return to clinic weekly until Day 28 (Week 4). Subjects will receive a refill of IL-2 (not at Week 4 visit) and the following measures will be obtained:

- Review of any new health problems, current medications, vital signs and weight,
- ECG,
- Blood draw (approximately 35 milliliters) will be drawn for
 - ✓ CBC with differential,
 - ✓ liver and kidney function panels,

- ✓ serum IL-2 levels,
- ✓ immune cell counts (Weeks 2 and 4)
- ✓ Week 4 only: CNI trough levels and serum pregnancy test (WOCBP)
- ✓ DSAs (Week 4)
- ✓ anti-IL-2 antibodies (Week 4)

Subjects will discontinue IL-2 treatment after Day 28 (Week 4).

Subjects will have blood drawn for standard of care labs at Week 4, i.e. CBC, liver and kidney panels, and CNI trough levels. We will obtain standard of care results from subjects' medical records and draw extra blood (approximately 25 ml) for research testing for DSA and anti-IL-2 antibodies (week 4), serum IL-2 levels and PBMCs flow cytometry and a serum pregnancy will be conducted for WOCBP.

Follow-up (W8, W12, W36)

Subjects will return to clinic for post-treatment follow-up at Weeks 8, 12 and 36. The following measures will be obtained:

- Review of any new health problems, current medications, vital signs and weight,
- Full physical examination will be completed at end of study (Week 36);

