- Review standard of care lab results for
 - ✓ CBC with differential,
 - ✓ liver and kidney function panels,
 - ✓ CNI trough levels,
- Blood draw (approximately 20 milliliters) for study labs
 - ✓ Immune cell counts (Weeks 8 and 12)
 - ✓ serum IL-2 levels (Weeks 8 and 12)
 - ✓ serum pregnancy test for WOCBP (Weeks 8 and 12).
 - ✓ anti-IL-2 antibodies (Week 36)

Dosage Reduction and Treatment Withdrawal

The dose of IL-2 may be reduced by half to 0.15 million IU /m² daily if a subject experiences untoward side effects. If symptoms improve, the dose may be re-escalated to target. If symptoms persist, the dose frequency may be reduced to every other day administration or the Investigator may discontinue study treatment.

Study treatment will be discontinued in the presence of any of the following circumstances:

- ✓ Subject withdraws consent
- ✓ Life threatening anaphylactic reaction to IL-2
- ✓ Life threatening infection on IL-2
- ✓ The Investigator may discontinued study treatment in the presence of other clinically significant findings including abnormal ECG, blood panel results >2x ULN and/or other signs of significant toxicities.

Subjects who are withdrawn from treatment will complete remaining study visits and continue to receive follow-up care from his/her BIDMC transplant Hepatologist.

Standard of Care Maintenance Immunosuppression: Eligible patients must be receiving stable dosing of immunosuppressant therapy for a minimum of 1 month prior to study enrollment. Maintenance immunosuppression is customize to the patient but typically, stable liver transplant patients at 2-4 year post transplant who are otherwise eligible to enroll into this trial would be taking tacrolimus (target 12 hour trough goal of 4-6ng/mL) with or without mycophenolic acid (as mycophenolate mofetil or mycophenolate sodium) at a dose between 500-1000mg twice a day.

Safety Monitoring

The PI is ultimately responsible for protecting the rights, safety and welfare of subjects enrolled into the trial. Study visits will be conducted weekly during the treatment phase of the trial; post treatment follow-up visits will be conducted at week 8 and 12. The PI will review all safety parameters including clinical safety laboratory assessments within 48 hours of completion of the measure. Clinical laboratory values that fall outside of the pre-specified safety ranges will be brought to the PIs attention the day the reports are final to assess clinical significance.

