- Review of essential documents in the regulatory binder for completeness and currency;
- Inspection of every (100%) informed consent form to assure that correct versions are used; that the names of subject and consenter are legible; that forms are properly signed and dated by subject and consenting physician investigator; and documentation is available to document consent procedures.
- Verification that every enrolled subject meets eligibility criteria;
- Review of a minimum of 10% of case report forms entered to source verify accuracy and completeness with specific attention to ...
 - ✓ Dose modifications
 - ✓ Adverse events, concomitant medications and intercurrent illnesses
 - ✓ Missed study visits, procedures, labs, etc
 - ✓ Drop out and withdrawals
- Review of all regulatory reporting
- Reporting findings to Sponsor/Investigator.

Table 1: Study Visits Schedule and Procedures

	Visit	Screening and Baseline		Treatment to Week 4					Follow-up to Week 36		
		Screening	Baseline Day 1	Day 3	W1	W2	W3	W4	W8	W12	W36
Study Procedures:	Visit #	1	2	3	4	5	6	7	8	9	10
Informed Consent		✓									
Full Physical Exam & Medical History		✓									✓
Limited Physical Exam & Medical History			✓	✓	✓	✓	✓	✓	✓	✓	✓
Vital Signs		✓	✓	✓	✓	✓	✓	✓	✓	✓	✓
Electrocardiogram (ECG)		✓			✓	✓	✓	✓			
Fibroscan		✓ ¹									
Study Blood Tests:											
Pregnancy test (for women of child bearing potential)		✓							✓	✓	✓
CBC with Differential			✓	✓	✓	✓	✓	✓	✓ ⁴	✓ ⁴	✓ ⁴
Liver panel (AST, ALT, AP, Total Bilirubin, Albumin)		✓ ²	✓	✓	✓	✓	✓	✓	✓ ⁴	✓ ⁴	✓ ⁴
Kidney panel (Na, K, Cl, CO2, Creatinine, Glucose, Ca)		✓ ²	✓	✓	✓	✓	✓	✓	✓ ⁴	✓ ⁴	✓ ⁴
Viral hepatitis and autoimmunity panels (HBVsAg, HCVAb, ANA, ASMA IgG)		✓ ³									
Immunosuppression drug level			✓						✓ ⁴	✓ ⁴	✓ ⁴
Immune cell counts			✓			✓			✓	✓	✓
IL-2 Blood level			✓		✓	✓	✓	✓	✓	✓	✓
T-cell exhaustion markers (only at baseline)			✓								
DSA (pre and post IL-2 treatment)			✓						✓		
Samples anti IL2 antibody testing			✓						✓		✓

¹ Only if a fibroscan or a liver biopsy was not completed for standard of care within the last 12 months

² Only if liver panel or kidney panel was not collected for standard of care within the last month

³ Only if viral and autoimmunity tests not completed for standard of care within past 6 months

⁴ Obtained as part of standard of care

B. Statistical Considerations

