Sample Size Justification: This is a pilot study to determine the efficacy and safety of very low dose IL-2 administration in a select group of liver allograft recipients. Investigators will consent as many as 12 subjects into the screening phase in order to treat not more than 10 patients from the BIDMC Transplant Institute's Liver Transplant Program.

The primary endpoint for the trial is the percent change in absolute numbers of regulatory T cells (Tregs) from pre-treatment baseline to end of treatment, i.e. the week 4 treatment visit.

For IL-2 to be clinically viable, we would require evidence that 60-80% of participants experience a biological response defined as a 2 fold increase in absolute number of Treg cells from baseline. Less than 50% of responding participants would be an unacceptable low response. The success of IL-2 will be defined based on a one sided 95% confidence interval (CI). The CI for a 0.80 response rate with 10 subjects would be 0.59-1.00 enabling exclusion of a response rate of 0.50.

Data Analysis: Differences in absolute numbers of circulating endogenous Treg cells from baseline to end of treatment will be compared using standard descriptive statistics and paired t-tests.

C. Subject Selection

Study subjects will be identified from the BIDMC Transplant Institute Liver Transplant Program by hepatologist [name] (Medical Director of the Liver Transplant Program) and surgeon [name] (Surgical Director of the Liver Transplant Program).

Inclusion criteria:

1. Adult liver transplant recipients 2-4 years post transplantation
2. Male or female, age \leq 65 years old
3. Stable dosage of immunosuppressant therapy for 1 month prior to study.

Exclusion criteria:

1. Recipient of multiple transplants (including solid organ, stem-cell, and bone marrow)
2. Serum liver panel (ALT, AST, Alkaline Phosphatase and Total Bilirubin) $> 2 \times$ ULN,
3. Serum creatinine $> 1.5 \times$ ULN,
4. eGFR of < 40 ml/min,
5. Detectable hepatitis viral load,
6. Abnormal ECG with clinically significant findings per study physician's judgement,
7. Active infection,
8. Presence or history of autoimmunity disorders,
9. Evidence of allograft rejection,
10. Liver biopsy or fibroscan evidence of advanced stage liver fibrosis ($>$ Stage 2 Fibrosis),
11. Presence or history of cardiac or pulmonary disease,
12. Pregnant or nursing (lactating) women,
13. Presence or history of seizure disorder,

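### Does the blank Week 4 cell for immune cell counts in Table 1 put the primary endpoint at risk?

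*Combined protocol and SAP*

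**What the plan says.** Section B3 B (Statistical Considerations) defines the primary endpoint as the percent change in absolute Treg number "from pre-treatment baseline to end of treatment, i.e. the week 4 treatment visit".

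The visit text in section B3 A gives the sampling times for that measurement:

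- Baseline/Treatment Visit Day 1 (W0) lists "immune cell counts".
- Treatment (W1, W2, W3, W4) lists "immune cell counts (Weeks 2 and 4". A later paragraph of the same section describes the extra research blood taken at Week 4 and names "serum IL-2 levels and PBMCs flow cytometry" among its uses.
- Follow-up (W8, W12, W36) lists "Immune cell counts (Weeks 8 and 12".

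Table 1 (Study Visits Schedule and Procedures) has a row "Immune cell counts". Matched to the column headings, its ticks fall at Baseline, W2, W8, W12 and W36. The row "DSA (pre and post IL-2 treatment" is ticked at Baseline and W8, whereas the visit text places DSA at Baseline and Week 4.

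**The concern.** A visit schedule is what coordinators tend to work from, and here its cell for the primary-endpoint visit is empty. Four other rows also lack a W4 tick that the visit text calls for: pregnancy test, immunosuppressant drug level, DSA and anti-IL-2 antibody. Five rows with the same gap look like more than one stray mark.

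A Treg count not taken at Week 4 cannot be replaced by the Week 8 count, because treatment stops after Day 28. With at most 10 treated subjects, each lost sample removes a tenth of the primary data. If an exact one-sided limit were used to exclude a 50% response rate, 8 of 9 or 7 of 8 responders would be needed once one or two subjects were lost. DSA sampled at Week 8 would also describe a different moment from the end of treatment.

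**Working it through.** **Step 1: Table 1 against the visit text.** The header order is "Screening Baseline Day 1 Day 3 W1 W2 W3 W4 W8 W12 W36". Each laboratory row was matched to it cell by cell and set beside the visit text.

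| Row | Visit text | Table 1 | Ticks, text / table |
|---|---|---|---|
| Immune cell counts | Baseline, W2, W4, W8, W12 | Baseline, W2, W8, W12, W36 | 5 / 5 |
| Pregnancy test | Screening, W4, W8, W12 | Screening, W8, W12, W36 | 4 / 4 |
| DSA | Baseline, W4 | Baseline, W8 | 2 / 2 |
| Anti-IL-2 antibody | Baseline, W4, W36 | Baseline, W8, W36 | 3 / 3 |
| Immunosuppressant level | Baseline, W4, W8, W12, W36 | Baseline, W8, W12, W36 | 5 / 4 |
| IL-2 level | Baseline, W1 to W4, W8, W12 | Baseline, W1 to W4, W8, W12, W36 | 7 / 8 |
| CBC | Baseline, W1 to W4, W8, W12, W36 | Baseline, Day 3, W1 to W4, W8, W12, W36 | 8 / 9 |

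In the first four rows the counts agree, and every misplaced tick sits exactly one visit late. For immune cell counts, a single slip of the last three ticks accounts for both the missing W4 and the extra W36. Rows ticked without a break up to W4 (CBC and IL-2 level above, and ECG) keep their W4 tick. A table read from PDF can lose position after a run of empty cells, so the pattern fits a reading error at least as well as a drafting error.

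The last three rows differ in count (5 against 4, 7 against 8, 8 against 9). Moving ticks sideways cannot repair that, so table and text do disagree there. None of the three is the Treg measurement.

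**Step 2: how often the Week 4 count is specified outside the table.** Three times: the treatment-visit list, the Week 4 research draw with flow cytometry, and the endpoint definition. Subjects attend at Week 4 and have research blood drawn in any case.

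**Step 3: the confidence limit.** The plan's figure for a 0.80 response rate with 10 subjects reproduces as a one-sided 95% Wald limit:

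0.80 − 1.645 × √(0.80 × 0.20 / 10) = 0.80 − 1.645 × 0.1265 = 0.592, stated as 0.59.

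The scheduling question does not enter this calculation.

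**Step 4: the thresholds for 9 and 8 subjects.** By the Wald method:

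- n = 10: 8/10 gives 0.592 and passes; 7/10 gives 0.70 − 1.645 × √(0.70 × 0.30 / 10) = 0.46 and fails.
- n = 9: 7/9 gives 0.778 − 1.645 × √(0.778 × 0.222 / 9) = 0.55 and passes.
- n = 8: 6/8 gives 0.75 − 1.645 × √(0.75 × 0.25 / 8) = 0.498 and fails; 7/8 gives 0.68 and passes.

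By exact binomial tails at a true rate of 0.50:

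- One non-responder: 11/1024 = 0.011 (n = 10), 10/512 = 0.020 (n = 9), 9/256 = 0.035 (n = 8). All are below 0.05.
- Two non-responders: 56/1024 = 0.055, 46/512 = 0.090, 37/256 = 0.145. All are above 0.05.

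The exact rule therefore allows one non-responder at each of the three sizes. The figures 8/9 and 7/8 describe ordinary missing data. A schedule error would remove the Week 4 count for every subject, not for one or two.

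**The case for a change.** The strongest argument for a change is that slippage does not explain the whole table. Three rows have the wrong number of ticks. The anti-IL-2 tick at W36 and the W4 ticks for ECG, CBC and IL-2 level are where the text puts them, and the footnoted standard-of-care ticks for drug levels line up with those of the CBC and liver rows at W8, W12 and W36. Nor does the protocol offer much that would catch an undrawn tube in time: laboratory staff are kept unaware of visit sequence, source verification is guaranteed for only 10% of case report forms, and monitoring cannot recover a sample. Correcting a table costs almost nothing.

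Part of this stands. The table and the text differ on the immunosuppressant level, the IL-2 level and the CBC, and someone should tidy them.

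The argument does not carry over to the primary-endpoint row. Slippage can occur row by row, so well-placed ticks elsewhere do not show that the immune count ticks are where the protocol's authors put them. The footnoted drug-level ticks are not decisive either, because the visit text also treats the Week 4 level as standard of care. Losing the endpoint would further require staff to disregard both the visit text and the endpoint definition, in a trial of at most 10 patients from one programme whose monitoring gives specific attention to missed laboratory tests.

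**Conclusion.** No change to the plan follows. The Week 4 Treg count is already required by the visit text and by the endpoint definition, and a team following them draws it. The blank W4 cell may be a product of reading the table from PDF; if it also stands in the source table, it is a clerical slip that the text resolves. It is enough to compare the tick positions with the source table and bring any that differ into line with the visit text.

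In size, three of the seven rows compared differ from the text by one tick each whatever the tick positions, and four more may only be displaced. The endpoint, the paired analysis and the 0.59 limit do not change. The conclusion assumes that staff work from the visit text as well as the table. If Table 1 alone were followed exactly as it reads here, 0 of up to 10 subjects would have the Week 4 count.

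### Women of childbearing potential are pregnancy-tested at Screening and not again until Day 28, the last dosing day; nothing requires a recent negative result before the first IL-2 dose

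*Combined protocol and SAP*

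**What the plan says.** Pregnancy testing is set out in the visit lists of section B3.A.

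- **Screening (S0):** "serum pregnancy test for women of child bearing potential (WOCBP"). Unlike the other laboratory panels, the Fibroscan and the ECG, this test has no allowance for an earlier result. It is done at Screening, after consent.
- **Baseline/Treatment Visit Day 1 (W0):** a separate, later visit: "Subjects will return to clinic to complete baseline measures and begin study treatment". Its blood list repeats the liver and kidney panels and adds blood count, immune, drug-level and antibody measurements. It has no pregnancy test.
- **Treatment (D3):** liver and kidney panels only.
- **Treatment (W1, W2, W3, W4):** "Week 4 only: CNI trough levels and serum pregnancy test (WOCBP").
- **Follow-up (W8, W12, W36):** "serum pregnancy test for WOCBP (Weeks 8 and 12").

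On timing, the plan states "Subjects will return to clinic weekly until Day 28 (Week 4") and "Subjects will discontinue IL-2 treatment after Day 28 (Week 4"). Drug is resupplied at the weekly visits: "Subjects will receive a refill of IL-2 (not at Week 4 visit").

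Exclusion criterion 12 (section C, Subject Selection) bars pregnant women. B5, Pregnancy and Fertility, requires a pregnancy test before the first dose, gives the unknown fetal effect of IL-2 as the reason, and requires contraception throughout the study. It also requires immediate reporting of a pregnancy and withdrawal if a test confirms it.

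**The concern.** The first dose is given at a later visit than the Screening test, and the plan does not say how much later that visit may be. The B5 requirement sets an order (test, then dose) but no recency. The look-back windows in the Screening list (1 month, 3 months, 6 months, 1 year) run backwards from Screening and concern other tests, so they do not limit the interval to Day 1.

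At stake is fetal exposure to a drug whose fetal effect the protocol itself calls unknown, in women the protocol intends to exclude. Once dosing has begun, the first scheduled test comes when almost all the drug has been given.

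**Working it through.** No sample-size or power figure bears on this point. The check is a count of visits and days.

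**Inputs.** One dose daily on Days 1 to 28, so 28 doses at full dosing (B3.A, Day 1 and W1–W4 text). Week 4 is Day 28 (same section). Tests are at Screening and Weeks 4, 8 and 12. The Screening-to-Day 1 interval, *s* days, is not stated.

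**Tests relative to dosing.** There are 4 scheduled tests: 1 before dosing, 0 on Days 1–27, 1 on the last dosing day and 2 afterwards. So 1 + 2 = 3 of 4 fall on or after the last dosing day.

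**Doses before the first repeat test.** Days 1–27 give 27 doses. Doses that the Day 28 result could still change: 28 − 27 = 1 if it is back before that day's injection, otherwise 0. The injection time is not stated. These are maxima: the dose-reduction rules permit every-other-day dosing, which would lower the counts.

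**Refills.** Three (Weeks 1, 2 and 3). None follows a repeat test.

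**Gap between the first two tests.** *s* + (28 − 1) = *s* + 27 days, with no upper limit on *s*. Illustrative values, all assumed:

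| *s* (days) | Age of negative result at first dose | Gap to next test |
|---|---|---|
| 7 | 7 | 34 |
| 14 | 14 | 41 |
| 30 | 30 | 57 |

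**With a Day 1 test.** The result is 0 days old at the first dose, or at most 3 days old under a 3-day window. The gap to Day 28 is 27 days, or at most 3 + 27 = 30. This removes the unlimited part of the gap; it does not add a test during Days 2–27.

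**With a Week 2 test as well** (Week 2 taken as Day 14, inferred from Week 4 being Day 28). Doses remaining after the sample:

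- result back before the Day 14 injection: 28 − 13 = 15;
- result back after it: 28 − 14 = 14;
- acted on only after the Day 16 dose: 28 − 16 = 12.

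The last case uses the full limit in Safety Monitoring: "The PI will review all safety parameters including clinical safety laboratory assessments within 48 hours of completion of the measure". That section also sends out-of-range laboratory values to the PI on the day they are final. Whether a positive pregnancy test counts as such a value is not stated, so 12 is the low end. The longest gap from Day 1 to Day 28 becomes max(14 − 1, 28 − 14) = 14 days.

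**The case against.** The strongest reply is that the plan already has layered protection: a pregnancy exclusion, a serum test that must be done at Screening, progression only without evidence of pregnancy, mandatory contraception and a duty to report. Staff also ask about new health problems on Day 1, Day 3 and at Weeks 1, 2 and 3, five contacts before Day 28. The course lasts four weeks, and no section sets a testing frequency that this schedule breaches.

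Much of this stands. These controls lower the risk, and they are why a mid-course test is a matter of choice. They do not close the Day 1 gap, because none is a test and none dates the Screening result. The for-cause test in B5 follows a reported pregnancy, so it cannot find one the woman has not recognised.

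A second reply concerns cost. The documents give no turnaround time for a serum test. Day 1 is also the baseline blood draw and the supervised first dose, so a late result could force a return visit or separate the baseline Treg sample from the first dose. This stands, and it is why the fix allows a sample shortly before Day 1.

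A reader might infer more than the documents support:

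- *That women are dosed untested.* They are not; the Screening test is mandatory.
- *That Table 1 contradicts the visit text.* Its columns may have shifted in extraction, so no such error is claimed and the table is not used as evidence.
- *That a fetal exposure is likely.* No pregnancy rate or number of WOCBP is given, so no probability can be stated.

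**Conclusion.** The point holds as a minor gap in the safety schedule. Followed exactly, the plan lets a woman who became pregnant after Screening receive her first dose, against its own exclusion. No scheduled test falls on Days 1–27, so up to 27 of 28 doses precede the first repeat test.

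The visit and dose counts follow from the visit text and assume full daily dosing. The 34-, 41- and 57-day gaps rest on assumed values of *s* and are illustrations. That a positive scheduled test would stop dosing is a reasonable inference: the B5 withdrawal rule is written around a reported pregnancy, and the treatment-discontinuation list in B3.A does not name pregnancy.

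A reader might conclude that Week 2 testing is also required. The documents do not support that; the firm finding is the missing recent test before the first dose. Severity stays minor because at most 10 subjects are treated, the number of WOCBP may be zero, the existing controls help, and neither the primary endpoint nor the sample size is touched.

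**What to change.** Add to the Day 1 (W0) list: *pregnancy test (WOCBP), negative result required before the first IL-2 dose*. If same-day results are not available, allow a serum test within a short stated window before Day 1, for example 3 days. Mark the test in Table 1.

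Optionally, add a test to the Week 2 blood already being drawn. At about 12–15 doses still avoidable, it is a low-cost addition at the investigators' discretion.

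Cost: one extra test per WOCBP, at most 10 in total if all treated subjects are WOCBP; two each with Week 2, at most 20. The operational price is that the first dose waits for the result, or that a separate sample is needed shortly before Day 1. The Week 2 option needs no extra visit or draw.
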